A Phase I Randomized Controlled Trial of a Positive Psychology Intervention for Patients With
Multiple Sclerosis

NCT03637699

Version 2.14.2018

DETAILED PROTOCOL

I. BACKGROUND AND SIGNIFICANCE

Living with multiple sclerosis (MS), a chronic autoimmune disease characterized by an unpredictable and variable course, presents a significant challenge for many patients. Depression and anxiety are common, occurring in up to 50% [1] and 35% [2] of patients, respectively. Health-related quality of life (HRQOL) is often impaired and has been shown to deteriorate following a relapse [3]. Positive psychological constructs such as positive affect, optimism and subjective well-being may play an important role in adaptation to chronic disease [4]. In patients with MS, positive constructs have been shown to be negatively associated with depression and anxiety [5-7] and positively associated with physical, social and psychological adjustment [7, 8]. A psychosocial intervention aimed at increasing positive constructs may facilitate adjustment and improve HRQOL in patients with MS.

Positive psychology (PP) uses targeted activities to increase the frequency and intensity of positive emotional experiences [9]. Targeted activities span several domains, including gratitude (e.g., systematically recalling positive life events), using one's personal strengths in a deliberate manner and altruism (e.g., performing acts of kindness). Two meta-analyses of PP interventions (PPI) demonstrated that these interventions significantly enhanced subjective well-being and were effective in reducing depressive symptoms in both depressed and non-depressed individuals. Studies that included multiple PP exercises were more effective than approaches that used a single activity. The benefits of PPI were sustained for periods of up to 6 months [10, 11].

Although there are a few studies of PP for individuals with medical illnesses, no RCT of PP has been published in MS. Members of our team have experience adapting PP interventions for medically ill patients including patients with acute cardiovascular disease, type 2 diabetes and MS and delivering them in research interventions. PP interventions are broadly applicable, require little provider training and the exercises are well-accepted and easy to complete. The development of an at home, phone-based PP intervention could represent a low cost, innovative and effective tool to increase positive affect in patients with MS. This may lead to decreases in depression, anxiety and fatigue and improvements in HRQOL and self-reported functional activities such as work.

II. SPECIFIC AIMS

This phase I randomized controlled trial (RCT) will examine the efficacy of an at home positive psychology (PP) training intervention to increase positive affect in patients with multiple sclerosis (MS). The RCT will include a five-week intervention phase and a five-week extension phase.

Specific Aim 1: Evaluate the tolerability and acceptability of a five-week at home PP training intervention for MS patients. We will assess the tolerability of the intervention by calculating the proportion of subjects who complete four of the five weekly exercises. We will determine the acceptability of each exercise by having subjects rate the ease and utility of each exercise after it is completed.

Specific Aim 2: Examine the efficacy of PP training to improve positive affect, emotional function, health-related quality of life (HRQOL), and self-reported functional activities. We will compare positive affect in subjects in the intervention and control group at the completion of the intervention phase. We will also assess between-group differences in depression, anxiety, fatigue, HRQOL and work productivity following the intervention phase.

Specific Aim 3: Determine if improvements in positive affect, emotional function, HRQOL and self-reported functional activities following PPI training are maintained. For subjects in the intervention group who demonstrate a benefit from PPI, we will determine if that benefit is maintained by comparing positive affect, depression, anxiety, fatigue, HRQOL and work productivity at the completion of the intervention and extension phases.

III. SUBJECT SELECTION

Thirty subjects with MS will be enrolled at the Partners MS Center. Subjects will be recruited from the Comprehensive Longitudinal Investigation of Multiple Sclerosis at the Brigham and Women's Hospital Partners MS Center: The CLIMB Study (1999P010435).

Inclusion criteria:

1. Diagnosis of clinically isolated syndrome or MS
2. Age 18-65
3. Able to read and write in English
4. Enrollment in the CLIMB study

Exclusion criteria:

5. Moderate or marked cognitive abnormalities on brief mental status testing identified by the treating neurologist during routine visits to the Partners MS Center that would preclude meaningful participation in the PP exercises

IV. SUBJECT ENROLLMENT

All CLIMB subjects being seen at the Partners MS Center for a routine clinical visit will be identified. They will be approached by their physician about participation in a PP study and will be given a study flyer. Additional flyers may be posted at the Partners MS Center. Interested individuals will be brought by their physicians to meet with a member of the research staff to learn about the study in more detail. They will be given a copy of the consent form to review. They will have the opportunity to discuss the study with their physician as well as other members of the research study staff prior to giving consent. Individuals will have at least 12 hours to consider participation. Consent will be obtained by study co-investigators or by the research coordinators listed on the protocol during the enrollment visit at the Partners MS Center.

V. STUDY PROCEDURES

This RCT will include an intervention phase (Phase I) and an extension phase (Phase II).

Enrollment Visit (60 minutes)

Subjects will be enrolled at the Partners MS Center at the Brigham and Women's Hospital. At enrollment, all subjects will be consented and assigned a study subject ID. Subjects will complete a battery of patient reported outcome (PRO) measures in REDCap, a secure web application for building and managing online surveys. The PRO measures include:

1. Positive and Negative Affect Scale (PANAS) [12] is comprised of two 10-item mood scales, one measuring positive affect and the other negative affect.
2. Life Orientation Test-Revised (LOT-R) [13] is a 6-item measure of optimism and pessimism and the most widely used measure of optimism.
3. Center for Epidemiologic Studies Depression Scale (CES-D) [14] is a 20-item self-report measure of depression that focuses on the cognitive and affective rather than the somatic components of depression.
4. State Trait Anxiety Inventory (STAI) [15] includes two 20-item questionnaires designed to measure the current temporary condition of “state” anxiety and the more general and long-standing quality of “trait” anxiety.
5. Modified Fatigue Impact Scale (MFIS) [16] is a 21-item questionnaire used to assess the impact of fatigue on physical, cognitive and psychosocial functioning.
6. Health Status Questionnaire (SF-36) [17] is a widely-used generic measure of HRQOL. It yields an 8-scale profile of functional health as well as physical and mental health summary scores.
7. Work Productivity and Activity Impairment Questionnaire (WPAI) [18] is a 6-item measure of health-related work productivity (absenteeism and presenteeism) as well as the effect of health problems on the ability to perform regular daily activities.
8. Perceived Stress Scale (PSS) is a 10-item measure of the degree to which situations are perceived as stressful [19].
9. Brief Resilience Scale (BRS) is a 6-item scale that measures the ability to bounce back or recover from stress [20].
10. State Optimism Measure (SOM) is a 7-item measure of “state” optimism or optimism at the present moment.

Using a computerized random number generator, subjects will be randomized to the intervention or control group.

Intervention Phase (5 weeks)

In the intervention phase (Phase I: Weeks 1-5), subjects randomized to the intervention group will be given a study participant manual and asked to set up a time for weekly phone calls with the study trainer. They will complete five weeks of PP exercises, one exercise per week. They will be asked to rate their mood prior to and after completing each exercise. They will also be asked to rate the ease and utility of each exercise. The weekly calls with the study trainer will be used to review the completed exercise and introduce the next exercise. These calls will be recorded so that a percentage (10%) of these recordings can be reviewed to ensure that the PP and goal-setting portions of the intervention are being delivered as described in the protocol and study trainer manual. The control group will have no study activities during intervention phase and will be considered a wait-list control. At the completion of the intervention phase, all subjects will be emailed a link to complete PRO measures in REDCap.

Extension Phase (5 weeks)

In the extension phase (Phase II: Weeks 6-10), subjects in the control group will receive their study participant manual in the mail. They will be contacted by the study trainer to set up weekly phone calls. They will complete the PPI as described above. The intervention group will complete no study activities in the extension phase. At the completion of the extension phase, all subjects will be emailed a link to complete PRO measures.

Intervention: The PP intervention consists of five weeks of PP training using the following exercises:

1. Gratitude for positive events: Recall three positive events that occurred in the past week and write about the events and how the events made you feel.
2. Personal strengths: Complete a brief survey of personal strengths and select a strength such as perseverance or humility and use it deliberately in the next 24 hours. Write about how you used the strength and how you felt while using it.
3. Gratitude letter: Recall another individual's kind act that resulted in joy, relief, serenity or other positive feelings. Write a letter to the person describing feelings of gratitude associated with this event.
4. Enjoyable and meaningful activities: Intentionally complete three acts in a single day – a pleasurable act done alone, a pleasurable act done with others and a meaningful or important act.
5. Remembering past successes: Focus on a time when you experienced success and write about the event and the positive feelings and thoughts you had during the event

These exercises have all been described by Huffman et al. [21]. Exercises may require anywhere from 15 minutes to several hours to complete.

The study trainer, [name], serves as the supervising research coordinator for two PP intervention trials in medically-ill populations. She has experience completing phone and in-person study assessments with patients who have medical illnesses for numerous studies. She works under the supervision of [name]. She will receive training utilizing our standard protocol (via review of didactic materials, role play, and director work with supervisors) and ongoing supervision from our director of behavioral interventions. She will also receive didactic teaching from MS experts on the basics of MS care and will have shadowed in the MS clinic to better understand MS patients' experiences. During the study, [name] or another physician study staff member will be available by phone or pager to intervene, if needed, due to subject discomfort or to answer specific questions about the study.

Two study manuals tailored to individuals with MS will be prepared: a study trainer manual and a study participant manual. At enrollment, subjects in the intervention group will be given the study participant manual and asked to schedule their first weekly phone call with the study trainer. The calls will last 45-60 minutes, and will be used by the study trainer to (a) review the weekly exercise and discuss the ease and utility ratings recorded by subjects after the exercise was completed; (b) discuss the rationale for the next exercise using a guided review of the study participant manual; and (c) describe the following week's exercise and brainstorm ways to complete it. Subjects in the control group will be mailed a copy of the study participant manual at the beginning of the extension phase of the study. This is to prevent subjects in the control group from completing the exercises during the intervention phase. They will be contacted by the study trainer to schedule their weekly phone calls. All subjects will complete PRO measures at enrollment, completion of the intervention phase and completion of the extension phase.

VI. BIOSTATISTICAL ANALYSIS

To assess the tolerability of the intervention (Specific Aim 1), our goal is to demonstrate that the proportion who will complete four out of five exercises is greater than 0.5. Given our sample size of 30 subjects, we will have 80% power to detect a difference if the true proportion of subjects who will complete four out of five exercises is 0.75 using a one sample binomial test of proportions (Stata routine: *power oneproportion*). For the comparison of the treatment groups in terms of PRO measures (Specific Aim 2), the intervention effect will be estimated using analysis of covariance (ANCOVA) model. In the ANCOVA model, the post-intervention scores will be compared between the groups controlling for baseline scores. All outcome measures (PANAS, LOT-R, CES-D, STAI, MFIS, SF-36, WPAI, PSS, BRS, and SOM) will be compared using the same model. To assess whether PPI benefits are maintained at 10 weeks (Specific Aim 3), we will first calculate the change from baseline to week 5 for each of the outcome measures. For the subjects who experience a benefit of the intervention, we will then assess if at least 50% of the benefit was maintained at the 10-week time point. The proportion of subjects who maintained the benefit will be reported.

VII. RISKS AND DISCOMFORTS

There are no major risks associated with participating in the study. Subjects may experience discomfort writing down and sharing emotional aspects of their lives. If they do experience discomfort, they may choose not to complete the weekly PP assignments. If they feel their participation is becoming too burdensome or is exacerbating ongoing symptoms, they have the option to decline further participation and withdraw from the study.

There is some potential for breach of confidentiality. No information will be shared with treatment providers unless a participant requires immediate assistance. In such cases, treatment providers will be informed and subjects will be referred to a mental health provider at the Partners MS Center.

VIII. POTENTIAL BENEFITS

This is a pilot study designed to determine the tolerability and efficacy of an at home PP training intervention for individuals with MS. If the results suggest that home PP training is tolerable and effective, it may advance the use of PP as a low cost, innovative and effective tool for increasing positive affect, decreasing depression and anxiety and improving HRQOL in patients with MS.

IX. MONITORING AND QUALITY ASSURANCE

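### Does the Aim 1 tolerability test need a written pass mark and a rule for controls who leave before they are offered the exercises?

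*Combined protocol and SAP*

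**What the plan says.** Section II defines the tolerability measure as "calculating the proportion of subjects who complete four of the five weekly exercises". Section VI turns it into a test: "our goal is to demonstrate that the proportion who will complete four out of five exercises is greater than 0.5". The power statement begins "Given our sample size of 30 subjects, we will have 80% power to detect a difference". Its alternative is a completion proportion of 0.75. The method is described as "using a one sample binomial test of proportions", and the Stata routine is named.

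Section III gives the enrolment: "Thirty subjects with MS will be enrolled at the Partners MS Center". Under section V, controls have nothing to do in weeks 1-5 and receive the participant manual only when the extension phase starts. The stated reason is: "This is to prevent subjects in the control group from completing the exercises during the intervention phase". Section VII says that subjects who find participation too burdensome may leave: "they have the option to decline further participation and withdraw from the study".

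No section states the significance level, whether the test is one- or two-sided, the number of completers needed, or whether a control who leaves before week 6 is a non-completer or is left out.

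**The concern.** The wording of section VI points two ways. The goal is directional (a proportion above 0.5), while the power is for detecting a difference, which suggests two sides. At N = 30 the two readings at 5% disagree at exactly one count, 20 completers. An analyst who saw that count could defend either conclusion.

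The second worry comes from the wait-list design. An N of 30 can be reached only by including the controls, yet a control who leaves in weeks 1-5 has had no chance to complete anything. Counting that person as a failure or excluding them can change the result. Aim 1 is the only aim with a power statement, so a loose rule here would undermine the one formal planning figure in the protocol.

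**Working it through.** **Inputs.** From section VI: null p0 = 0.5, alternative p1 = 0.75, N = 30, stated power 80%, one-sample binomial test. From section III: 30 enrolled in total. Assumed, because the documents give no figure: the number w of controls lost before week 6.

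**1. Reproduce the 80%.** For each usual level, take the smallest count r whose upper tail P(X ≥ r | 30, 0.5) is within the level (half the level if two-sided). The power is then P(X ≥ r | 30, 0.75).

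| Level | r | Tail at 0.5 | Power at 0.75 |
|---|---|---|---|
| One-sided 5% | 20 | 0.0494 | 89.4% |
| Two-sided 5% (or one-sided 2.5%) | 21 | 0.0214 | 80.3% |
| One-sided 1% | 22 | 0.0081 | 67.4% |
| Two-sided 1% | 23 | 0.0026 | 51.4% |

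Only the second row matches. A normal-approximation score test at two-sided 5% agrees:

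power = Φ[(√30 × 0.25 − 1.96 × 0.5) / √(0.75 × 0.25)] = Φ[(1.369 − 0.980) / 0.433] = 81.6%.

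Its smallest passing count is also 21, since z = 2.19 at 21/30 and 1.83 at 20/30. Other two-sided 5% approximations lie further from 80%: 75.4% with a continuity correction and 88.5% for a Wald test.

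**2. Does N = 30 need both groups?** Yes. If an assumed 15 intervention subjects alone were counted, the exact cut-off would be 12 of 15, with power 46.1%. The stated 80% therefore includes controls.

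**3. The count in dispute.** With 20 of 30, p = 0.049 one-sided and 2 × 0.0494 = 0.099 two-sided. With 21 of 30, the two-sided p = 2 × 0.0214 = 0.043. The probability of exactly 20 at a true 0.75 is 0.8943 − 0.8034 = 0.0909, or 9.1%. The conclusion is ambiguous there only if the one-sided 5% test is still open, and step 1 shows that it does not give the plan's power.

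**4. Early leavers (hypothetical w).** Take 0.75 as the completion proportion among those offered the exercises, with the exact two-sided 5% test.

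| w | Counted as failures (21 of 30 needed) | Excluded (cut-off) |
|---|---|---|
| 0 | 80.3% | 80.3% (21/30) |
| 1 | 71.3% | 71.3% (21/29) |
| 2 | 60.0% | 75.0% (20/28) |
| 3 | 47.1% | 64.3% (20/27) |

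With one loss the rule makes no difference to power. With two it can reverse a result: 20/28 has tail 0.0178, so two-sided p = 2 × 0.0178 = 0.036, against 0.099 for 20/30. If 0.75 instead refers to all enrolled subjects and all 30 stay in the denominator, power is 80.3% whatever w is.

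**The case for a change.** The case for asking for a change is that it would cost a few sentences and no subjects. It would also remove the need to work backwards from a power figure. The directional goal in section VI does give some cover for a one-sided reading, and the treatment of early leavers cannot be recovered from the text at all. The thirty in section III is planned enrolment and the 30 in section VI is the N for power; neither defines an analysis set.

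The last point stands: the plan does not settle the denominator, and it would be wrong to say that it implies all 30. But that also weakens any prescribed remedy. Scoring a control who never received the manual as a tolerability failure guards against flattering exclusions, yet that person tells us nothing about tolerating the exercises. Restricting to those offered the exercises fits the aim more closely but departs from everyone enrolled. Reasonable statisticians differ on this, and the loss scenarios that give the choice its weight are assumed.

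The sidedness argument is thinner. It needs the investigators to adopt a level that contradicts their own stated power.

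**Conclusion.** No change to the plan is needed. The stated 80% is correct, and it identifies the test: at least 21 of 30, two-sided 5% or one-sided 2.5%, exact power 80.3%. This rests on considering only the usual significance levels and on 0.75 applying to the 30 analysed.

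The handling of controls who leave before week 6 is a real omission, but one that analysts can fill sensibly. The numbers enrolled, offered the exercises and completing at least four allow both proportions to be reported with exact intervals. The size of the issue cannot be fixed from the documents: it is nil with no early losses, and it could decide a borderline result with two.

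Section VIII describes a pilot, and no section ties a go/no-go decision to this test. Writing the rule down would be tidy, but it would correct no wrong figure and offer no better method.

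### Does entering the WPAI as a single outcome, with no score or employed subset named, leave the functional-activities analysis in need of repair?

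*Combined protocol and SAP*

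**What the plan says.** Section II (Specific Aims) gives self-reported functional activities as one target of Aims 2 and 3. The outcomes then listed name work only. For Aim 2: "We will also assess between-group differences in depression, anxiety, fatigue, HRQOL and work productivity following the intervention phase". For Aim 3, restricted to intervention-group subjects who benefit, the plan is "comparing positive affect, depression, anxiety, fatigue, HRQOL and work productivity at the completion of the intervention and extension phases".

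Section V describes the WPAI more broadly. It "is a 6-item measure of health-related work productivity (absenteeism and presenteeism) as well as the effect of health problems on the ability" to carry out ordinary daily activities. Everyone fills it in: "All subjects will complete PRO measures at enrollment, completion of the intervention phase and completion of the extension phase".

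Section VI puts every instrument through one ANCOVA of the post-intervention score adjusted for the baseline score: "All outcome measures (PANAS, LOT-R, CES-D, STAI, MFIS, SF-36, WPAI, PSS, BRS, and SOM) will be compared using the same model". For Aim 3, "we will first calculate the change from baseline to week 5 for each of the outcome measures"; the plan then reports the share of benefiting subjects who keep at least half of the gain at week 10.

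The eligibility list in Section III covers diagnosis, age 18–65, English literacy, CLIMB enrollment and cognitive status. It does not mention employment.

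**The concern.** The aims, the instrument description and the analysis section differ in scope. The aims say work productivity, Section V describes two work components and one daily-activity component, and Section VI says only WPAI. Absenteeism and presenteeism have no value for a subject without a job. The documents do not say so, but it follows from the terms. The work comparisons would therefore rest on an unstated fraction of 30 subjects, while the daily-activity comparison could use all of them.

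Two things seem to be at stake. First, the functional result could be taken from whichever of three scores looked best, each with its own denominator. Second, the only functional outcome named in the aims is the one with fewest subjects and least precision. In Aim 3, a subject with no work score also has no change to classify as a benefit.

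**Working it through.** **The plan's own figure.** The only power statement in Section VI concerns Aim 1: N = 30, null proportion 0.5, true proportion 0.75, power 80%. Assuming a two-sided 0.05 level (the plan states none), the score test gives Φ[(0.25 − 1.96·√(0.25/30)) / √(0.1875/30)] = Φ[(0.25 − 0.179)/0.0791] = Φ(0.90) = 81.6%. The exact rule of at least 21 of 30 gives 80.3%. The figure is reproduced, and it does not involve the WPAI.

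**Selecting among scores.** With independent scores each tested at 0.05, the chance of at least one false positive is:
- two work scores: 1 − 0.95² = 9.8%;
- all three: 1 − 0.95³ = 14.3%.

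Correlation lowers the three-score figure. Simulated ANCOVAs (normal scores, baseline correlation 0.5, 15 per arm for daily activity, 6 to 15 per arm for the work scores) gave 12.7–13.6% at a between-score correlation of 0.5, 11.1–12.6% at 0.7 and 10.2–11.8% at 0.8. These rates apply only if a success on any one score is treated as the result.

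**Context.** Section VI lists ten instruments and no multiplicity adjustment. With one score each and independence, 1 − 0.95¹⁰ = 40.1%. Two more WPAI scores make twelve tests: 1 − 0.95¹² = 46.0%. Several other instruments also have more than one score, on the protocol's own description: PANAS has two scales, STAI two, and SF-36 eight scales plus two summaries.

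**Precision.** Assume equal arms, two-sided 0.05 and 80% power. The standardised difference has SE = √(4/N)·√(1 − ρ²), and the detectable difference comes from the noncentral t with N − 3 degrees of freedom. The documents give neither ρ nor an employed share, so both are assumptions. At ρ = 0.5:

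| Subjects with the score | SE | Detectable difference (SD) |
|---|---|---|
| 30 (all) | 0.316 | 0.92 |
| 24 (80%) | 0.354 | 1.04 |
| 18 (60%) | 0.408 | 1.22 |
| 15 (50%) | 0.447 | 1.37 |
| 12 (40%) | 0.500 | 1.57 |

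Over ρ from 0.7 to 0, the range is 0.76–1.06 SD for 30 subjects and 1.30–1.82 SD for 12. These values depend on N, the employed share and ρ. Naming a score changes none of them.

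**Who enters each analysis.** The ANCOVA needs a baseline and a week-5 value, so a work-score comparison can contain only subjects with both. Aim 3 starts from intervention-group subjects who show a benefit. A subject with no work score cannot show one and does not enter that denominator. For most subjects, then, the stated methods already fix the analysis set.

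**The case for a change.** The strongest case for a change is that two competent analysts could both follow the protocol and present different functional results. One might lead with presenteeism in the employed, the other with daily-activity impairment in everyone. The WPAI also differs from the other instruments: part of it cannot be scored for some eligible subjects, and its description is wider than the outcome the aims name for it. A sentence of wording would cost nothing, since all components are collected.

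Much of this stands. The gap is real, and the job-dependent denominator is specific to the WPAI. A small ambiguity also remains for a subject who stops working between assessments: Section VI does not say whether someone with a work benefit at week 5 and no work score at week 10 is left out or counted as not maintained.

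It does not amount to a defect in the plan. Section VI commits to comparing all the outcome measures, and two analysts who do that will produce the same set of estimates; they could differ only in emphasis. The one substantive step on offer, making daily-activity impairment the lead functional score and work supportive, would override the outcome that both aims name. It would gain subjects and give up the outcome the investigators chose. That trade-off is theirs to make, and the documents do not show their choice to be wrong. Nor could the daily-activity maintenance proportion be taken over all randomized subjects, because Aim 3 covers the intervention group only and controls receive the intervention in weeks 6–10.

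**Conclusion.** The plan leaves a definition unwritten, and its analysts can fill it sensibly: compare each WPAI component in the subjects who have it at the required visits, and show the number per arm beside each result. Done that way, the plan as written gives no wrong result.

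The 10–14% false-positive figure is conditional on choosing among scores after seeing the data, which nothing in the text provides for. Even then it concerns one of ten instruments in a 30-subject pilot with no multiplicity adjustment across them. The wider detectable effects for the work scores rest on assumed employment of 40–80%, equal arms and an assumed baseline correlation, and would be the same under any wording. Aim 1, its stated power and the positive-affect comparison are untouched. Stating the score and its denominator would be a courtesy to the reader; the plan does not need to change.

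### The Specific Aim 3 proportion who kept at least half their benefit is expected to be about 50% or more with no intervention effect and no drift, so without a benchmark it cannot be read at face value

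*Combined protocol and SAP*

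**What the plan says.** Section VI, on Specific Aim 3, starts from individual changes: "we will first calculate the change from baseline to week 5 for each of the outcome measures". It continues: "For the subjects who experience a benefit of the intervention, we will then assess if at least 50% of the benefit was maintained" at 10 weeks. The only output is one figure per outcome: "The proportion of subjects who maintained the benefit will be reported". No size of change is given that would count as a benefit, and no reference value or interval accompanies the proportion.

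Section II places the question in the intervention arm ("For subjects in the intervention group who demonstrate a benefit from PPI, we will determine if that benefit is maintained") and says it will be answered "by comparing positive affect, depression, anxiety, fatigue, HRQOL and work productivity at the completion of the intervention and extension phases". The 50% rule appears only in Section VI.

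Two features of Section V matter here. The data are collected at three times in everyone: "All subjects will complete PRO measures at enrollment, completion of the intervention phase and completion of the extension phase". The untreated comparison ends at week 5. Up to then, "The control group will have no study activities during intervention phase and will be considered a wait-list control"; in weeks 6-10 the same subjects receive the intervention ("They will complete the PPI as described above").

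**The concern.** A subject's observed change mixes any true effect with measurement noise and ordinary fluctuation. Those who look improved at week 5 tend to have had a chance-low baseline, a chance-high week-5 score, or both. At week 10 they fall back from the high score, but they are still measured against the low baseline, so part of the apparent gain seems to be kept. If scores also wander slowly, some of the change really does persist, although the intervention did not cause it.

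The natural reading of a result such as 60% maintained is that most of those helped stayed helped. If an intervention that did nothing is expected to give a figure of that order, the reading is unsafe. The proportion is Section VI's whole answer to a stated aim.

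**Working it through.** The plan gives no figure for Aim 3 to reproduce. Its one power figure (80%) belongs to Aim 1 and does not bear on this point.

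**Inputs from the documents.** Three visits (baseline, week 5, week 10); selection on the week-5 change; the 50% rule; 30 subjects in total.

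**Assumptions.** Normal scores with equal variances (SD = 1), higher scores better, and a constant effect d in SD units. Correlation between adjacent visits is r = 0.5 to 0.8. The baseline-to-week-10 correlation is either r (equal correlations) or r² (AR(1)). Benefit means any improvement, and there is no drift, unless stated.

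**Step 1: restate the rule.** Keeping at least half means Y10 − Y0 ≥ 0.5(Y5 − Y0), that is, Y10 ≥ (Y0 + Y5)/2. Put D = Y5 − Y0 and M = Y10 − (Y0 + Y5)/2. The reported quantity estimates P(M ≥ 0 | D > cut-off).

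**Step 2: equal correlations, no effect.** Cov(D, M) = r − r = 0, so selection on D tells us nothing about M. M has mean 0, so the proportion is exactly 50% for any r and any cut-off.

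**Step 3: AR(1), no effect.** Cov(D, M) = r − r² = r(1 − r), Var(D) = 2(1 − r) and Var(M) = (1 − r)(1.5 + r). Hence corr(D, M) = r/√(3 + 2r), and the proportion is 1/2 + arcsin(corr)/π.
- r = 0.5: corr = 0.5/√4 = 0.25, giving 58.0%.
- r = 0.6: 59.5%.
- r = 0.7: corr = 0.7/√4.4 = 0.334, giving 60.8%.
- r = 0.8: 62.2%.

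With a benefit cut-off of 0.5 SD, the bivariate normal CDF gives 61.5%, 64.0%, 66.8% and 70.4% in the same order.

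**Step 4: with an effect.** Under equal correlations Var(M) = 1.5(1 − r), so the proportion is Φ(mean(M)/√(1.5(1 − r))). Mean(M) is +d/2 if the effect is kept, 0 if half lost and −d/2 if lost. For d = 0.5 and r = 0.7, kept is Φ(0.25/√0.45) = Φ(0.373) = 65%. The AR(1) values come from the bivariate normal CDF.

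| Scenario, r = 0.7 | Equal correlations | AR(1) |
|---|---|---|
| No effect | 50% | 61% |
| 0.5 SD effect, kept | 65% | 68% |
| 0.5 SD effect, half lost | 50% | 56% |
| 0.5 SD effect, fully lost | 35% | 43% |

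An intervention that never worked is expected to score higher than one whose 0.5 SD effect disappeared.

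**Step 5: drift.** With drift of s per period and no effect, mean(M) = 2s − s/2 = 1.5s. At r = 0.7, s = −0.2 SD gives Φ(−0.3/0.671) = 33% (equal) or 48% (AR(1)); s = +0.2 SD gives 67% or 73%.

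**Step 6: a week-5 to week-10 comparison in the same responders.** Here selection biases towards apparent loss. E[Y10 − Y5 | D > 0] is the retained change plus Cov(Y10 − Y5, D)/SD(D) × φ/Φ, evaluated at mean(D)/SD(D), with covariance −(1− r) under equal correlations and −(1 − r)² under AR(1). With a 0.5 SD effect fully kept, the expected change is still −0.12 to −0.26 SD (equal) or −0.02 to −0.13 SD (AR(1)) over r = 0.5 to 0.8. Dropping the 50% rule while keeping the selection would therefore not solve the problem.

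**The case against.** The strongest reply is that Aim 3 presupposes an effect. It asks whether gains from the training last, and whether there are gains is settled by the randomised Aim 2 ANCOVA. Given an effect, the proportion orders kept, half lost and lost correctly under both correlation structures. This stands, and a reader who inferred that the proportion carries no information would go too far. But the plan does not make Aim 3 conditional on Aim 2, and even with an effect the figure has no stated scale.

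Three other inferences should be resisted.
- That no effect always outscores a half-lost effect. It does so under AR(1), but under equal correlations both give 50%.
- That noise explains everything. Under AR(1), the excess over 50% reflects slow change that really persists but was not caused by the intervention. That is a problem of attribution, and arm means share it after week 5.
- That Sections II and VI contradict each other. The 50% rule can fairly be read as making Section II's comparison subject by subject.

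It is also fair to say that this is a 30-subject pilot and that no test or success criterion is attached to the proportion. No type I error problem follows. That limits the harm but does not make the raw figure interpretable.

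**Conclusion.** The point holds as a matter of interpretation and is worth fixing. With no effect and no drift, about half or more of the apparent responders are expected to be reported as having maintained a benefit. The 50% value under equal correlations needs no particular r or cut-off. The higher values (58-62%, or 62-70% with a 0.5 SD cut-off) need AR(1) with r = 0.5 to 0.8. None of these is a universal benchmark: drift of ±0.2 SD per period at r = 0.7 moves the figure across 33-73%, and the documents supply none of the required quantities.

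The consequence is modest. A reader might infer that a false efficacy claim could result, but the documents do not support that, because efficacy is judged by the between-group ANCOVA and Aim 3 only reports a proportion.

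**What to change.** In Section VI, under Specific Aim 3:

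- For each outcome, add the mean week-10 minus week-5 change and the mean week-10 minus baseline change, with 95% CIs, in all subjects randomised to the intervention arm, without selection on the week-5 change. Align the population wording of Aim 3 in Section II.
- Base the maintenance statement on both estimates together, read only alongside the Aim 2 result and the wait-list arm's baseline-to-week-5 change, which is the only untreated estimate of drift. A week-10 minus week-5 change near zero with no Aim 2 effect is not maintenance, and a non-significant change is not proof of it.
- Keep the responder proportion as descriptive only. Define benefit, give the denominator, and note that about 50% or more is expected with no effect and no drift.

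The three assessments are already collected, so the cost is wording. There are three downsides.

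- The intervals are wide. With 15 subjects in the arm (1:1 allocation and no dropout assumed) and r = 0.7, the half-width for week 10 minus week 5 is 2.145 × √(0.6/15) = 0.43 SD (0.55 at r = 0.5, 0.35 at r = 0.8). Power to detect complete loss of a 0.5 SD effect is about 64% at r = 0.7. For week 10 minus baseline under AR(1), the half-width is 2.145 × √(1.02/15) = 0.56 SD.
- There is still no untreated comparator after week 5.
- An arm mean answers a slightly different question from whether those who benefited kept the benefit, which is why the proportion stays as a descriptive figure.
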